6.11 GI perforation/fistula and non-GI fistula formation

GI perforation/fistula and non-GI fistula formation have been reported with cabozantinib and other approved drugs that inhibit VEGF pathways.

After starting cabozantinib, subjects should be monitored for early signs of GI perforation such as abdominal pain, nausea, emesis, constipation, and fever especially if known risk factors for developing GI perforation or fistula are present.

- Discontinue cabozantinib treatment in participants diagnosed with GI or non-GI perforation/fistula. Nivolumab can be resumed after perforation/fistula has healed.

6.12 Treatment-emergent hypertension

Guidelines for hypertension management:

- For patients who require a delay of greater than 6 weeks for management of hypertension, discontinue cabozantinib.
- Patients may have up to 3 agents for management of hypertension prior to any dose reduction in cabozantinib.
- 24 to 48 hours should elapse between modifications of anti-hypertensive therapy.
- Treating physicians should not add antihypertensive medications that are strong inducers or inhibitors of CYP3A4.

Criteria for dose modification	Intervention
--	---------------------

> 140 mm Hg (systolic) and < 160 mm Hg OR > 90 mm Hg (diastolic) and < 110 mm Hg
	
Maintain dose of cabozantinib and nivolumab; however, please see below for recommendations regarding anti-hypertensive therapy.
 
Recommended Antihypertensive Therapy
 
 • Increase existing antihypertensive therapy or initiate a new antihypertensive agent if needed after 24-48 hours of treatment; increase dose in stepwise fashion every 24-48 hours until BP is controlled or at the maximum dose of therapy. • If BP is still not controlled, add another antihypertensive agent; increase dose of this drug as described in Step 1. • If BP is still not controlled, add a 3rd agent; increase dose of this drug as described in Step 1. • If BP is still not controlled after maximal medical management, proceed with one dose level reduction.

≥ 160 mm Hg (systolic) OR ≥ 110 mm Hg (diastolic)
	
Maintain dosing of nivolumab.
 
Delay cabozantinib until systolic BP ≤ 159 mmHg and diastolic BP ≤ 99 mmHg. Once blood pressure is controlled to this level, resume cabozantinib with one dose level reduction and consider the recommended antihypertensive therapy outlined above.
 
For patients who require a delay of greater than 6 weeks for management of hypertension, discontinue cabozantinib.
 
If the patient requires hospitalization for management of symptomatic systolic BP >180 or diastolic BP >110, then discontinue cabozantinib and recommend inpatient management as clinically indicated with IV medications. Maintain dosing of nivolumab. Delay cabozantinib until systolic BP ≤ 159 mmHg and diastolic BP ≤ 99 mmHg. Once blood pressure is controlled to this level, resume cabozantinib with one dose level reduction and consider the recommended antihypertensive therapy outlined above.
 
NOTE: Discontinuing or reducing the dose of cabozantinib is expected to cause a decrease in BP. The treating physician should monitor the patient for hypotension and adjust the number and dose of antihypertensive medication(s) accordingly.

Hypertensive crisis or hypertensive encephalopathy
	
Discontinue cabozantinib treatment.
 
Hold nivolumab until resolution.

BP, blood pressure.

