6.8 Stomatitis and Mucositis

Refer to Section 5.4 for guidance regarding supportive care of mucositis and stomatitis.

For **grade 2 mucositis or stomatitis that is subjectively tolerable**, continue cabozantinib and nivolumab in addition to providing supportive care.

For **grade 2 mucositis or stomatitis that worsens, lasts ≥ 10 days, or interferes with adequate nutrition (and supportive care is insufficient)**, continue nivolumab but delay cabozantinib until toxicity improves to grade ≤ 1 , then resume cabozantinib with one dose level reduction.

For **grade 3 mucositis or stomatitis that interferes with adequate nutrition (and supportive care is insufficient)**, continue nivolumab but delay cabozantinib until toxicity improves to grade ≤ 1 , then resume cabozantinib with one dose level reduction.

For **grade 4 mucositis or stomatitis that interferes with adequate nutrition (and supportive care is insufficient)**, discontinue cabozantinib permanently, resume nivolumab when toxicity improves to grade ≤ 1 .

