6.21 Endocrinopathy including hypophysitis and adrenal insufficiency

Note all patients with symptomatic pituitary enlargement, exclusive of hormone deficiency, but including severe headache or enlarged pituitary on MRI or aseptic meningitis or encephalitis should be considered grade 3 events. Isolated thyroid or testosterone deficiency may be treated as grade 2 if there are no other associated deficiencies and adrenal function is monitored.

Table: Management of Endocrinopathy including hypophysitis and adrenal insufficiency

Grade	Management
≤ 2	Asymptomatic abnormalities do not require dose delay*. If symptomatic, hold until on a stable replacement hormone regimen. If treated with steroids patients, must be stable off of steroids for two weeks with the exception of adrenal replacement therapy.
3	Hypophysitis: Hold nivolumab and cabozantinib* until \leq Grade 1, then resume at same dose. Other endocrinopathies: Hold nivolumab and cabozantinib* until \leq Grade 1 and stable on replacement hormones, then resume at same dose.

4	
Discontinue nivolumab.
 
Discontinue cabozantinib. If the subject was unequivocally deriving clinical benefit, the subject may be able to resume cabozantinib at a lower dose as determined by the investigator.

---	--

*Patients must be evaluated to rule out pituitary disease prior to initiating thyroid replacement, and steroids including baseline serum: cortisol, ACTH, TSH and free T4

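### Section 6.12 tells sites both to discontinue cabozantinib and to delay and then resume it for the same event, a hospitalization for symptomatic hypertension

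*Combined protocol and SAP*

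**What the plan says.** The relevant row of the section 6.12 table applies from 160 mm Hg systolic or 110 mm Hg diastolic. Its cell has two parts that matter here.

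- **General case.** Nivolumab continues. For cabozantinib: "Delay cabozantinib until systolic BP ≤ 159 mmHg and diastolic BP ≤ 99 mmHg". Then: "Once blood pressure is controlled to this level, resume cabozantinib with one dose level reduction". The 6-week limit follows: "For patients who require a delay of greater than 6 weeks for management of hypertension, discontinue cabozantinib". The same limit also stands in the guideline list above the table.
- **Hospitalized case.** For a patient admitted with symptomatic systolic pressure above 180 or diastolic above 110, the paragraph opens: "then discontinue cabozantinib and recommend inpatient management as clinically indicated with IV medications". It then continues nivolumab and repeats the delay and resume sentences of the general case word for word.

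The next row, for hypertensive crisis or encephalopathy, says "Discontinue cabozantinib treatment", gives no restart step, and holds nivolumab until resolution.

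**The concern.** One paragraph attaches two cabozantinib instructions to one event. Nothing distinguishes when each applies: there is no benefit test, no split between a first and a recurrent episode, and no named decision-maker. A site that acts on the first sentence stops the drug. A site that acts on the later sentences gives it again at a lower dose.

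What is at stake is whether a patient admitted for severe hypertension is re-exposed to cabozantinib. Section 7.1.1 lists hypertension among the drug's expected effects, so the event is foreseeable. The protocol also provides for external sites (sections 4.3, 4.4 and 12.3), so the cell may be read independently by different teams.

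**Working it through.** No arithmetic applies beyond comparing thresholds. The check sets the instructions side by side.

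1. **Do the two branches cover the same patients?** Systolic above 180 implies at least 160, and diastolic above 110 implies at least 110. Every patient in the hospitalized branch therefore also meets the row's general entry criterion.

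2. **Do the branches differ in the restart rule?** No. Both use 159 systolic and 99 diastolic, and both restart one dose level lower.

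3. **What if delay-and-resume governs?** The hospitalized branch then leads to the same cabozantinib action as the general branch. The word *discontinue* has no separate effect.

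4. **What if discontinue governs?** The delay and resume sentences that follow it in the paragraph cannot apply. On a reading that gives *discontinue* its own meaning, one part of the paragraph is inoperative whichever part is followed.

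5. **How does section 6.12 use the two words?** Under the 6-week rule, discontinuation follows a delay that has lasted too long, so it is a different step from a delay. The crisis row uses *discontinue* with no restart. Section 6.13 draws a similar line: grade 2 or 3 venous thrombosis needing anticoagulation leads to a delay, while recurrence after restarting, or a grade 4 event, leads to discontinuation.

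6. **Is the usage uniform across the protocol?** No.
   - Section 6.8, for grade 4 mucositis, adds an explicit qualifier: "discontinue cabozantinib permanently, resume nivolumab when toxicity improves to grade".
   - Section 5.4.1, on drugs that prolong QTcF, also speaks of permanent discontinuation, which implies that there can be another kind.
   - Section 6.21, for grade 4 endocrinopathy, allows a restart after the word: "Discontinue cabozantinib. If the subject was unequivocally deriving clinical benefit, the subject may be able to resume cabozantinib at a lower dose". That restart depends on a stated benefit condition and on the investigator's determination. Section 6.12 has neither.

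7. **Is it an artefact of text extraction?** Nothing suggests so. The sentences are complete and in sequence.

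**The case against.** The strongest reply is that the paragraph describes a sequence: stop the drug, treat the patient in hospital, keep nivolumab going, wait for the pressure to fall, restart at a lower dose. On that reading *discontinue* means a temporary stop. The uses in sections 5.4.1, 6.8 and 6.21 lend it some support, and it may be what the sponsor intends. It does not settle the matter, because the paragraph does not say so and section 6.12 itself separates the two words.

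The second reply is that section 6.1 requires any restart after a dose interruption to be discussed with the PI. This is a real safeguard, and a reader who inferred that sites have nothing to guide them would go too far. But it does not say which sentence governs, and a site that reads *discontinue* as final may never raise the question.

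A reader might also infer that the cell decides whether the patient is classified as off protocol treatment. The documents do not show this. Nivolumab continues in this branch, section 6.1 allows the two agents to be modified independently when attribution is clear, and stopping cabozantinib alone is not among the criteria in section 5.5.

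**Conclusion.** The point stands as an internal contradiction in a safety instruction. It is not a criticism of a design choice. The text as written supports two courses of action for one severe event, and nothing in the protocol ranks them.

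**Size.** Only patients hospitalized for symptomatic hypertension above the stated thresholds are affected. The documents give no rate for this event, so the number is unknown, and enrolment is at most 35 (section 5.1). The consequence is possible inconsistency between sites in re-exposure to cabozantinib, moderated by the PI discussion in section 6.1.

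**What it does not touch.** The two-stage response-rate design in section 16.2 and its error rates do not depend on this cell. Tumor assessments continue through dose holds and delays (section 10, tumor assessment footnote).

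**What should not be read into it.** Because the hospitalized branch repeats the general rule, a reader might conclude that the repetition is a copying slip and that discontinuation was meant. That is possible, but the documents do not establish it: the sponsor may equally intend the same cabozantinib action in both cases. The conclusion here rests only on the wording, and on section 6.12's own contrast between delay and discontinuation.

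**What to change.** The sponsor should reconcile the sentences in this cell so that the hospitalized case carries one unambiguous cabozantinib instruction. The result should be checked against the 6-week rule and the hypertensive-crisis row. Nivolumab should be part of that check: it continues in one row and is held in the next, and section 6.12 gives no pressure or symptom definition that separates the two categories. Which action applies is for the sponsor to decide.

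The cost is an edit to one table cell, processed as a protocol modification under section 14 (review by both drug suppliers and the IRB) and notified to external sites under Appendix D. Sample size, endpoints and analyses do not change.

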6.13 Thromboembolic Event

Maintain dosing of nivolumab.

For **grade 2 or 3 venous thrombosis requiring anticoagulation**, delay cabozantinib. If the planned duration of full dose anticoagulation is ≤ 2 weeks, then delay cabozantinib until

anticoagulation is completed. If the planned duration of full dose anticoagulation is > 2 weeks, then resume cabozantinib during anticoagulation therapy if all of the following are met:

- The patient must be on a stable dose of LMWH prior to restarting cabozantinib. Warfarin or a novel oral anticoagulation drug may not be used for anticoagulation.
- The patient must not have any pathological condition that carries a high risk of bleeding.
- The patient must not have had any hemorrhagic events while on study.

For **recurrent/worsening venous thromboembolic events after resuming cabozantinib**, discontinue cabozantinib.

For **grade 4 venous thromboembolic events**, discontinue cabozantinib.

For **any grade arterial thromboembolic events including cerebrovascular ischemia, cardiac ischemia/infarction, peripheral or visceral arterial ischemia**, discontinue cabozantinib.

6.14 Hemorrhagic Events

Maintain dosing of nivolumab.

For **grade 2 CNS or pulmonary hemorrhage**, discontinue cabozantinib.

For **any other grade 3 or 4 hemorrhage**, discontinue cabozantinib.

6.15 Proteinuria

Proteinuria is an expected AE with the inhibition of VEGF pathways and has been observed in cabozantinib clinical studies. Nephrotic syndrome has been reported with cabozantinib and other inhibitors of VEGF pathways.

Management of Proteinuria:

Severity of Proteinuria (UPCR)	Management of Proteinuria
$\leq 1 \text{ mg/mg}$ ($\leq 113.1 \text{ mg/mmol}$)	
 • No change in protocol treatment or monitoring
$> 1 \text{ and } < 3.5 \text{ mg/mg}$ ($> 113.1 \text{ and } < 395.9 \text{ mg/mmol}$)	
 • Consider confirming with a 24-h protein assessment within 7 days • Continue nivolumab dosing • No change in cabozantinib treatment required if UPCR $\leq 2 \text{ mg/mg}$ or urine protein $\leq 2 \text{ g/24 h}$ on 24-h urine collection. • Dose reduce or interrupt cabozantinib treatment if UPCR $> 2 \text{ mg/mg}$ on repeat UPCR testing or urine protein $> 2 \text{ g/24 h}$ on 24-h urine collection. Continue cabozantinib on a reduced dose if UPCR decreases to $< 2 \text{ mg/mg}$. Consider interrupting cabozantinib treatment if UPCR remains $> 2 \text{ mg/mg}$ despite a dose reduction until UPCR decreases to $< 2 \text{ mg/mg}$. Restart cabozantinib treatment at a reduced dose after a dose interruption. • Repeat UPCR within 7 days and once per week. If UPCR $< 1 \text{ mg/mg}$ on 2 consecutive readings, UPCR monitoring can revert to protocol-specific times. (Second reading is confirmatory and can be done within 1 week of first reading.) If UPCR remains $> 1 \text{ mg/mg}$ and $< 2 \text{ mg/mg}$ for 1 month or is determined to be stable ($< 20\%$ change) for 1 month, check urine protein/creatinine per protocol or as clinically indicated.
$\geq 3.5 \text{ mg/mg}$ ($\geq 395.9 \text{ mg/mmol}$)	
 • Interrupt cabozantinib and nivolumab treatment pending repeat UPCR within 7 days and/or 24-h urine protein. • If $\geq 3.5 \text{ mg/mg}$ on repeat UPCR, continue to interrupt cabozantinib and nivolumab treatment and check UPCR every 7 days. If UPCR decreases to $< 2 \text{ mg/mg}$, restart nivolumab and cabozantinib treatment at a reduced dose and monitoring of urine protein/creatinine should continue weekly until the UPCR decreases to $< 1 \text{ mg/mg}$. If UPCR remains $> 1 \text{ mg/mg}$ and $< 2 \text{ mg/mg}$ for 1 month or is determined to be stable ($< 20\%$ change) for 1 month, check urine protein/creatinine per protocol or as clinically indicated. • If treatment is delayed for more than 6 weeks due to proteinuria, discontinue cabozantinib and nivolumab treatment.
Nephrotic syndrome	
 • Discontinue cabozantinib and nivolumab treatment.

RCC, renal cell carcinoma; UC, urothelial carcinoma; UPCR, urine protein/creatinine ratio.

6.16 Hypophosphatemia

Hypophosphatemia has been reported during treatment with cabozantinib.

Mild hypophosphatemia is usually asymptomatic or symptoms can be non-specific such as weakness, bone pain, rhabdomyolysis, or altered mental status. Other causes of hypophosphatemia such as poor nutrition, chronic alcoholism, malabsorption, excessive antacid use, glucocorticoids use, kidney dysfunction, respiratory alkalosis, vitamin D deficiency should be ruled out and/or these causes treated according to standard of care.

Mild to moderate hypophosphatemia should be managed by oral replacement including food that are high in phosphate (diary items, meats, beans) and/or oral phosphate supplements according to standard clinical practice guidelines.

6.17 Osteonecrosis of the Jaw

To minimize the risk of osteonecrosis of the jaw, it is recommended that, if possible, cabozantinib be stopped at least 4 weeks prior to dental procedures such as tooth extractions, implants, and major jaw surgery whenever possible. Cabozantinib does not need to be held for routine dental fillings and cleanings.

6.18 QTcF Prolongation

For **QTcF interval > 500 msec**, (confirm with triplicate EKG) continue nivolumab but delay cabozantinib, stop any medications that may prolong the QTcF interval (if possible), and consider checking calcium, potassium, and magnesium levels and correcting any abnormalities. Once QTcF interval \leq 500 msec, correction of electrolyte abnormalities has been considered, and symptoms have resolved, cabozantinib may be resumed with one dose level reduction.

6.19 Pulmonary Toxicity

Mild-to-moderate events of pneumonitis have been reported with nivolumab. Patients will be assessed for pulmonary signs and symptoms throughout the study. Patients will also have CT scans of the chest at every tumor assessment.

Management of pneumonitis is as summarized in the following table:

Grade	Management
≤ 1	Continue protocol therapy if radiologic findings only; dose may be held for further evaluation per investigator discretion
2	Hold nivolumab pending evaluation. Patient should discontinue nivolumab if prolonged steroids are required unless an alternative etiology of findings is identified. Withhold cabozantinib until resolved to \leq Grade 1.
3	Discontinue nivolumab. Withhold cabozantinib until resolved to \leq Grade 1.
4	Discontinue nivolumab. Withhold cabozantinib until resolved to \leq Grade 1.
Distinguishing inflammatory pneumonitis is often a diagnosis of exclusion for patients who do not respond to antibiotics and have no causal organism identified including influenza. Most patients with respiratory failure or hypoxia will be treated with steroids. Bronchoscopy may be required and analysis of lavage fluid for lymphocytic predominance may be helpful. Patients with new lung nodules should be evaluated for sarcoid like granuloma. Please consider recommending seasonal influenza inactivated vaccine for all patients.	

6.20 Neurologic Events

The principal treatments for neurologic toxicity are dose delay, corticosteroids, and IV immunoglobulin. Patients with any CNS events including aseptic meningitis, encephalitis, symptomatic hypophysitis, myopathy, peripheral demyelinating neuropathy, cranial neuropathy (other than peripheral n. VII), Guillain-Barre syndrome, and myasthenia gravis should discontinue nivolumab. If reversible posterior leukoencephalopathy syndrome (RPLS) is diagnosed then discontinue cabozantinib.

Table: Management of Neurologic Events

Grade	Management
≤ 1	Continue protocol therapy
2	Hold nivolumab. Hold cabozantinib. If treatment with steroids is required, permanently discontinue nivolumab. If no treatment with steroids is required, and it has resolved to \leq Grade 1, resume nivolumab and cabozantinib at same dose. Participants are permitted to resume treatment with nivolumab for peripheral isolated CN VII (Bell's palsy) when stable.
3	Discontinue nivolumab. Hold cabozantinib. If the subject was unequivocally deriving clinical benefit, the subject may be able to resume cabozantinib at a lower dose as determined by the investigator.
4	Discontinue nivolumab. Hold cabozantinib. If the subject was unequivocally deriving clinical benefit, the subject may be able to resume cabozantinib at a lower dose as determined by the investigator.

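### For grade 3 symptomatic hypophysitis, section 6.20 stops nivolumab while section 6.21 holds it and then resumes it at an unchanged dose

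*Combined protocol and SAP*

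**What the plan says.** Section 6.20 (Neurologic Events) has a paragraph and a graded table. The paragraph carries no grade limit. It opens with "Patients with any CNS events including aseptic meningitis, encephalitis, symptomatic hypophysitis" and runs on to its instruction: "symptomatic hypophysitis, myopathy, peripheral demyelinating neuropathy, cranial neuropathy (other than peripheral n. VII), Guillain-Barre syndrome, and myasthenia gravis should discontinue nivolumab". The table is graded:

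- Grade 1 or lower: therapy continues.
- Grade 2: both drugs are held. "If treatment with steroids is required, permanently discontinue nivolumab"; without steroids, and once the event is at grade 1 or lower, both drugs resume.
- Grades 3 and 4: nivolumab is discontinued, and only cabozantinib may be resumed, at a lower dose, if there is clear benefit.

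Section 6.21 (Endocrinopathy including hypophysitis and adrenal insufficiency) has a grading note and its own table. The note says that symptomatic pituitary enlargement, "including severe headache or enlarged pituitary on MRI or aseptic meningitis or encephalitis should be considered grade 3 events". The table reads:

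- Grade 2 or lower: "If symptomatic, hold until on a stable replacement hormone regimen"; steroid-treated patients "must be stable off of steroids for two weeks with the exception of adrenal replacement therapy".
- Grade 3: "Hypophysitis: Hold nivolumab and cabozantinib" until grade 1 or lower, "then resume at same dose".
- Grade 4: nivolumab is discontinued.

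Neither section refers to the other. Section 6.1 says that the most stringent instruction applies where several do, and explains stringency as the largest dose reduction. Section 6.2 permits dose reductions for cabozantinib only.

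**The concern.** A site that opens 6.20 for a patient with grade 3 symptomatic hypophysitis is told to stop nivolumab. A site that opens 6.21 for the same patient is told to restart it after recovery. The case that matters most is hypophysitis with aseptic meningitis or encephalitis: 6.20 lists both conditions among the events that end nivolumab, while the 6.21 note puts such pituitary cases in the grade that resumes.

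At stake is consistent handling of re-exposure after an immune-related pituitary or central nervous system event. The protocol provides for external sites (section 4.3, Appendix D), and Appendix D requires departures from the defined procedures to be reported. Here a site that follows one section to the letter departs from the other.

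**Working it through.** No figure in the plan bears on this point, so the check sets the texts side by side. Nivolumab action for symptomatic hypophysitis:

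| Grade | 6.20 paragraph | 6.20 table | 6.21 | Result |
|---|---|---|---|---|
| 1 or lower | discontinue | continue | if symptomatic, hold until hormone replacement is stable | 6.20 disagrees with itself |
| 2, no steroids | discontinue | hold, then resume | hold until hormone replacement is stable | 6.20 disagrees with itself; its table and 6.21 both hold first |
| 2, steroids given | discontinue | discontinue permanently | hold until off steroids and stable for two weeks, adrenal replacement excepted | conflict, less certain |
| 3 | discontinue | discontinue | hold to grade 1 or lower, then resume at an unchanged dose | clear conflict |
| 4 | discontinue | discontinue | discontinue | agree |

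**Grade 3.** The conflict does not depend on how 6.20 is read, because its paragraph and its table give the same answer. Both sections name hypophysitis, so neither is a residual category.

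**Grade 2 with steroids.** This is less certain because the 6.21 row for grade 2 or lower names neither hypophysitis nor a drug, and resumption is only implied by the instruction to hold.

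**Does anything else in the protocol settle it?**

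1. *Section 6.1, most stringent instruction.* Its natural sense favours stopping. But it measures stringency by dose reduction, and 6.2 gives nivolumab none. The bullet before it concerns several adverse events, not one event under two sections. Applied here, it would also leave the explicit grade 3 hypophysitis instruction in 6.21 with no effect for symptomatic cases.
2. *Section 6.1, discussion of restarts with the PI.* This adds a check but gives the PI no rule to apply.
3. *Section 5.5, item 4.* Treatment stops if toxicity has not come down to a tolerable grade 2 or lower within 6 weeks, unless benefit is unequivocal. This removes slow recoveries only.
4. *Section 6.1, 8-week limit.* Therapy ends if treatment is withheld for more than 8 weeks from the last dose. With nivolumab every 2 weeks, infusions due at weeks 2, 4 and 6 can be missed and the latest restart is week 8: at most 3 missed infusions.
5. *Appendix B.* The endocrinopathy and neurological algorithms are figures that are not visible in this text, so nothing can be concluded from them. Section 6.1 describes the algorithms as recommended.

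The two instructions therefore differ in effect only for patients who recover in time to satisfy items 3 and 4. For those patients, nothing visible says which one applies.

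**The case against.** A reader might infer that 6.20 stops nivolumab for symptomatic hypophysitis at every grade, and so that two of the three grade rows in 6.21 conflict with it. The documents do not support that. It rests on the ungraded paragraph alone, whereas the table beneath continues therapy at grade 1 or lower and allows nivolumab to resume at grade 2 without steroids. The 6.21 row for grade 2 or lower largely concerns hormone deficiency managed by replacement, since the note moves symptomatic pituitary enlargement to grade 3.

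The strongest remaining arguments are these.

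- *Discontinuation is not always final in this protocol.* Section 6.12 tells sites to discontinue cabozantinib and then describes resuming it, and the grade 4 row of 6.21 does the same. This weakens reliance on the 6.20 paragraph. It carries less weight for the 6.20 grade 3 row, which separates discontinuing nivolumab from holding cabozantinib and offers a way back for cabozantinib only.
- *Section 6.1 already decides the matter, and no restart happens without the PI.* The direction of 6.1 is conceded. Its wording still does not fit nivolumab, and PI discussion supplies a decision-maker rather than a decision.
- *Appendix B may state the intended action.* It may. That is a reason to check it, and it would not remove the contradiction from the body text.
- *Discontinuation for everyone would be a preference.* This stands for hormone-replaced patients at grade 2 or lower: the documents give no reason to override the 6.21 rule for them. Nor do they justify rewriting 6.1 for every toxicity in section 6.

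**Conclusion.** The concern holds at grade 3. For symptomatic hypophysitis, 6.20 stops nivolumab and 6.21 resumes it, and pituitary cases with aseptic meningitis or encephalitis fall on both sides. That is one of the three grade rows in 6.21, with high confidence. Steroid-treated grade 2 hypophysitis is a second conflict with lower confidence: it assumes that the unnamed drug in the 6.21 row includes nivolumab and that the 6.20 table applies to hypophysitis. Below grade 3, the 6.20 paragraph and table also disagree with each other. Grade 4 is consistent for nivolumab.

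The practical reach is small. It is confined to patients who recover within the 6-week and 8-week limits, out of at most 35 treated, and the documents give no incidence from which to estimate a count. The safeguards lower the risk without choosing an action. The response-rate endpoint, the sample size and the 18 + 17 decision rule are untouched. The conflict should be fixed because it concerns re-exposure after a serious immune-related event and is cheap to remove.

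**What to change.** 1. In 6.21, state that hypophysitis with aseptic meningitis or encephalitis follows 6.20, so nivolumab is discontinued.
2. For other grade 3 symptomatic hypophysitis, and for steroid-treated grade 2 hypophysitis, give one nivolumab action, identical in 6.20 and 6.21, with a cross-reference. The sponsor either keeps discontinuation and changes 6.21, or deliberately chooses hold-and-resume and removes symptomatic hypophysitis from the 6.20 list.
3. Until the amendment, tell sites that the more stringent action, discontinuation, applies at grade 3.
4. Check that the endocrinopathy and neurological algorithms in Appendix B give the same action.

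Leave unchanged the 6.21 rule for hormone deficiency at grade 2 or lower, under which treatment waits for stable replacement. Section 6.1 need not be rewritten.

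The cost is a few sentences and table entries at the next amendment, plus an interim note to sites. The downside is that an occasional patient may stop nivolumab who could have resumed it.
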